Exclusion Criteria: 1) any unstable medical condition or medical contraindication to moderate physical exertion (e.g., unstable angina or cardiac arrhythmia), 2) pregnancy, 3) currently taking Buprenorphine or recently stopped taking (within 1 month), 4) presence of cognitive impairment or language barrier that impairs full autonomy in the consent process or in the ability to participate in detailed interviews, 5) implants in the head or neck, cochlear implants, or pacemaker, 6) head or neck metastasis or recent ear trauma, 7) history of seizures.

6) **Study-Wide Recruitment Methods***

All recruitment will be in accordance with the Health Insurance Portability and Accountability Act (HIPAA), by the SCCC Protocol Review and Monitoring Committee and by the UM Department of Physical Therapy Research Leadership Team.

Black and Hispanic patients with persistent pain will be recruited for a 2-phased mixed methods study. Flyers will be placed in Uhealth clinics (Uhealth Physical Therapy, Uhealth Advanced Pain Management Center, and Sylvester Comprehensive Cancer Center) to recruit patients with neuropathic pain. In addition, the patient census of specific UHealth clinics (i.e., [name] medical oncology clinic, the Sylvester Posner Lymphema Clinic, and the Uhealth Pain Physical Therapy Clinic) will be used for recruitment. *Physicians will be informing participants first about the study before a member of the study team will be contacting patients.* Telephone numbers and/or emails of potential participants and they will be called to screen for inclusion. Patients who provide verbal consent to be

contacted for research purposes will be called by one of the research assistants.

The Sylvester Behavioral and Community-Based Research (BCSR) Shared Resource will be used to assist with recruitment of patients with chemotherapy induced peripheral neuropathy (CIPN).

7) Study Design

Primary Purpose: Other. This study will utilize principles of community-based participatory research to develop and test educational materials for consenting people to neurostimulation research.

Study Phase: N/A

Interventional Study Model: Parallel

Number of Arms: 2

Masking: Subject only

Allocation: Randomized

Enrollment: 28

8) Study Timelines*

Each participant will complete 3 visits for a total of ~10 hours, and it is expected that the visits are completed within 1-2 weeks of each other. Thus, participants will be enrolled for less than 3 weeks on average.

9) Study Endpoints*

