Participants will be given the choice to complete this first visit in person or via Zoom in order to decrease participation burden. For the second phase, all participants will receive active taVNS, but only Group 2 will receive both active and sham taVNS in a randomized crossover design.

All participants will first complete a pretrial assessment battery, followed by a 60-minute trial of taVNS applied with continuous monitoring of HRV during quiet sitting, and then concluded with a posttrial assessment. The second phase will be completed in two sessions that are anticipated to last ~4 hours each. In summary, participants will complete 3 visits for a total of ~10 hours to complete the study.

	Visit 1	Visit 2	Visit 3
taVNS video (n=12)	Education and baseline	Active taVNS	1-wk follow up
Brochures only (n=12) 6 participants	Education and baseline	Active taVNS	Sham taVNS
6 participants	Education and baseline	Sham taVNS	Active taVNS

A detailed description of each procedure is provided below:

*EXPECT questionnaire*⁷: The EXPECT is a 4-item questionnaire that assesses expectations for pain improvement. Each of the 4 items is scored on an 11-point scale, with 0 being no change and 10 representing complete relief. It is anticipated that this questionnaire will take less than 5 minutes to complete.

Heart rate variability (HRV): HRV will be measured with an H10 chest strap device (Polar, Finland) and will serve as the primary endpoint for response to taVNS in Aim 2. Participants will wear the chest strap continuously throughout the application of taVNS.

taVNS: A portable taVNS Stimulator (Soterix Medical, Woodbridge, NJ) will be used with flexible hydrogel electrodes to administer taVNS at the cymba concha (Figure 2), using monophasic pulses (pulse width:500 μ s; frequency 10 Hz), and delivered up to 200% of the perception threshold, but kept below the pain threshold, for 60 minutes. This device is approved for research purposes, and these parameters have been shown to maximize cardiovagal response with taVNS.⁸ Participants will be quiet sitting in a comfortable chair during the application of taVNS.

Figure 2. taVNS electrode application

Please see the Risks to Subjects section for procedures performed to lessen the probability or magnitude of risks.

12) Data Management*

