The principal investigator will be responsible for all data management and analyses. A research assistant will assist with data entry and qualitative data coding. All quantitative data will be entered and stored in the University of Miami REDCap system. NVivo 12 software (QSR International, United States) will be used for qualitative data management and analyses, and SPSS version 28 (IBM, United States) will be used for quantitative analyses (i.e., descriptive statistics).

13) Provisions to Monitor the Data to Ensure the Safety of Subjects*

Safety information will be collected during the taVNS trial study visit for this research and entered into Velos for tracking. All adverse effects will be reported to the study team, the IRB, and to the SCCC Data & Safety Monitoring Committee. All research activities will be stopped in the case

of a single serious adverse reaction (i.e., seizure) or if 3 or more minor adverse reactions (e.g., skin irritation from electrodes) are observed. A corrective plan (e.g. change in TMS or taVNS protocol) must be approved by the study team, IRB, and SCCC Data & Safety Monitoring Committee before research activities can be resumed.

The plan might include establishing a data monitoring committee and a plan for reporting data monitoring committee findings to the IRB and the sponsor.

14) Community-Based Participatory Research*

Prior to initiating research activities, a 4-member community advisory board (CAB) will be assembled, consisting of 2 people from each ethnicity (non-Hispanic African American and Hispanic), and the CAB will meet 4 times over the course of the year to provide general feedback on the project design, plan, and progress, including feedback on video scripts, final video products, and video dissemination plan. At least 1 person from each ethnic group on the CAB must have chronic pain (n≥2).

15) Sharing of Results with Subjects*

NA

16) Setting

Participants will be recruited from Sylvester Comprehensive Cancer Center, UHealth Physical Therapy, and from the UHealth Advanced Pain Management Clinic.

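### Read literally, the stopping rule in Section 13 lets a serious reaction other than a seizure be reported without triggering a stop

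*Combined protocol and SAP*

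**What the plan says.** Section 13 of the combined protocol and SAP makes three provisions.

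- **Reporting.** "All adverse effects will be reported to the study team, the IRB, and to the SCCC Data & Safety Monitoring Committee". This applies whatever the type or severity of the event.
- **Stopping.** The whole study halts in the event "of a single serious adverse reaction (i.e., seizure) or if 3 or more minor adverse reactions (e.g., skin irritation from electrodes) are observed". There are two triggers: one event in the serious class, or three in the minor class.
- **Restarting.** A corrective plan "must be approved by the study team, IRB, and SCCC Data & Safety Monitoring Committee before research activities can be resumed".

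The section defines neither class. It gives no third trigger, such as a stop at the committee's discretion. Its only other remark on oversight is a general one, that a data monitoring committee might be set up.

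Section 11 (procedures) refers elsewhere for risk reduction: "Please see the Risks to Subjects section for procedures performed to lessen the probability or magnitude of risks". That section was not in the text available for this review.

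**The concern.** The stop sentence treats its two classes differently. Skin irritation is offered as an example of a minor reaction. Seizure is given as what a serious reaction is. If staff take that as a definition, a serious reaction of any other kind falls between the triggers: it is not a seizure, and it is not minor.

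At stake is what must happen before the next stimulation session. After a seizure, everything stops until three bodies approve a corrective plan. After a different serious reaction, Section 13 requires only a report. The protocol does not say that sessions would continue; it leaves the decision to judgement at the time, which a stopping rule set in advance is meant to avoid.

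The protocol itself gives reason to think beyond seizure. The stimulation settings were chosen for their cardiac vagal effect (Section 11), the primary outcome is change in heart rate variability (Section 9), and people with pacemakers or unstable cardiac conditions are excluded (Section 5). Section 5 also excludes anyone with a history of seizures, so the one serious event named is one for which people with a known history are already screened out.

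**Working it through.** No statistical calculation applies, and the plan gives no error rate or derivation for its thresholds of 1 and 3. The check is to apply the rule as worded to different events, and then to count the sessions it covers.

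**Step 1. Apply the triggers.** Trigger A is "of a single serious adverse reaction (i.e., seizure"). Trigger B is "if 3 or more minor adverse reactions (e.g., skin irritation from electrodes) are observed".

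| Event | Reported? | Trigger A met? | Trigger B met? | Stop and approved plan required? |
|---|---|---|---|---|
| 1 seizure | Yes | Yes | No | Yes |
| 3 minor reactions | Yes | No | Yes | Yes |
| 1 serious reaction, not a seizure (e.g., a serious arrhythmia) | Yes | No, with *i.e.* read as 'that is' | No: not minor, and one event rather than three | No |

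For serious reactions other than seizure the section states no number at all, because the threshold of 3 belongs to minor reactions. If everything other than seizure were counted as minor, three such events would stop the study, but a single one still would not.

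**Step 2. Is the literal reading reasonable?** The protocol mostly keeps the two abbreviations apart. It uses *i.e.* to specify: the two modalities in Section 3, the qualifying pain complaints in Section 5, the named clinics in Section 6. It uses *e.g.* to illustrate: neuropathy causes and unstable conditions in Section 5. There is a counterexample close by: Section 12 uses *i.e.* to describe the quantitative analyses as descriptive statistics, although the aims in Section 3 state comparative hypotheses. Usage is therefore mixed. The contrast inside the stop sentence itself favours the literal reading but does not prove that it was intended.

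**Step 3. Sessions covered.** Inputs are the visit table in Section 11 (12 participants per group) and Section 7 ("Enrollment: 28").

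- Video group: 12 × 1 active = 12 sessions.
- Brochure group: 12 × (1 active + 1 sham) = 24 sessions.
- Total: 12 + 24 = 36, of which 12 + 12 = 24 are active and 12 are sham.
- With 28 enrolled and an assumed 14/14 split: 14 × 1 + 14 × 2 = 42, of which 28 are active and 14 are sham.

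These counts describe the scope of the rule and do not measure risk.

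**The case against.** The strongest reply is that the gap exists on one reading only, and probably not the intended one. The main words of the trigger name a class, serious adverse reactions, and the parenthesis may simply name the one such reaction the authors foresaw. A rule that stops everything for three skin irritations was hardly meant to ignore a graver event, and the loose *i.e.* in Section 12 shows the drafting is not strict. This stands as evidence about intent. It shows that the sentence is ambiguous, but it does not supply a rule that closes the gap.

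Second, the Risks to Subjects section may contain a wider stopping rule. That is possible and could not be checked. However, Section 11 cites that section for reducing risk, and Section 13 does not refer to it for stopping.

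Third, oversight is not absent. Every adverse effect goes to the same three bodies that must approve a restart, and they could act. That is correct, but Section 13 requires no pause while they consider the event.

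Fourth, changing the abbreviation alone would still leave 'serious' undefined. This also stands, and it is why the fix needs a definition as well.

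Finally, no endpoint, analysis or sample size is affected. That limits the weight of the point but does not remove it, because the sentence is a safety decision rule that staff would apply.

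**Conclusion.** The concern holds as a point about the wording of Section 13. Read literally, the section requires a stop after 1 seizure or 3 minor reactions, and states no threshold for any other serious reaction. Such a reaction must be reported, but neither a halt nor an approved corrective plan is required by that section. The wording applies to 36 sessions in the visit table (42 on the 14/14 assumption).

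The conclusion rests on reading *i.e.* as a definition. Its practical consequence also depends on there being no wider rule in the Risks to Subjects section. It does not show that the authors intended the narrow rule or that staff would carry on after a serious event. With no rate of serious reactions in the documents, nothing can be said about how likely the case is. The change should be made because the ambiguity sits in a safety rule and is cheap to remove. Confidence is medium.

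**What to change.** In the stop sentence of Section 13, replace the serious trigger with *any serious adverse reaction (e.g., seizure)*, and state that serious has the IRB's standard definition. Keep the word *reaction*, so that serious events unrelated to study procedures do not halt the research. If the Risks to Subjects section already has a wider rule, refer to it from Section 13 and make the two agree.

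This is an edit to one sentence, with the definition and, where needed, a cross-reference. The downside is a possible pause after a serious non-seizure reaction that, read literally, now needs only a report. It would last until the study team, the IRB and the SCCC monitoring committee approve a corrective plan. If the authors always meant any serious reaction, the edit only states their intent.

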19) Confidentiality

Confidentiality will be maintained by assigning participant identification numbers at the beginning of the study. All data will be identified using these ID numbers. The personal information included as data will consist of the gender, age, race, ethnicity, and cancer type and treatment. This information will be kept in a locked file cabinet and stored in a password-protected digital file on the encrypted database at the University of Miami Physical Therapy Department located at [name]. Signed consent forms will be kept in a master file in a locked file cabinet. Only the principal investigator and research assistant will have access to participant's personal information and data.

20) Provisions to Protect the Privacy Interests of Subjects

Participants will only interact directly with their respective Uhealth providers for recruitment (i.e., a Uhealth provider who already has access to the patient census would contact the patient for study recruitment, and the data collection will be

performed by investigators who are members of the Uhealth clinical team). Thus, the intrusiveness of participation is minimized.

Only IRB approved research team members will have access to study records. Overall study results will not be shared with study participants, individually. Confidentiality will be maintained by assigning subject identification numbers at the beginning of the study. All data will be identified using these ID numbers. This information will be kept in a locked file cabinet and stored in a password-protected digital file on the encrypted database in the office of the PI in the University of Miami Department of Physical Therapy located at [name]. Signed consent forms will be kept in a master file in a locked file cabinet. Only the principal investigator and research assistant will have access to subject's personal information and data.

21) Compensation for Research-Related Injury

Compensation will not be provided for research-related injury. Funds to compensate participants for pain, expenses, lost wages, and other damages caused by injury are not available. However, treatment will be available in most cases and their insurance may be billed or participants will have to pay.

22) Economic Burden to Subjects

There are no direct costs associated with participating in this study. However, transportation and parking may be an economic burden on some participants. Participants will be paid \$250 to compensate them for the economic and time burden (\$50 upon completion of visit 1 and \$200 for completion of visit 2).

23) Consent Process

We will follow SOP: Informed Consent Process for Research (HRP-090). The consent process will begin with the phone screening. If they provide verbal consent to the phone screening and are deemed eligible for the study, then they will be invited to the Lynn Center. At the Lynn Center, they will be educated on the study and provided with a written consent form to review and sign. The consent form and all research documents will be available in English and Spanish. Several of the research team members are bilingual and each participant will be consented in-person in the language which they are most comfortable. Potential participants will have the opportunity to consult with family members or others and will have all questions addressed by the PI or other members of the study team. Potential participants will be briefed on their rights as a research subject, including their right to withdraw at any time with no negative consequences.

The study procedures will be reviewed with each participant at each phase of the study (i.e., tVNS and TMS procedures will be reviewed after completion of the mixed methods phase and prior to initiating the trial phase) and verbal consent will be re-obtained to ensure ongoing consent.

Each time that the verbal consent is obtained, it will be reiterated to the patient that they may choose to withdraw from the study at any time.

Non-English-Speaking Subjects

All study documents will be available in English and Spanish. A bilingual study team member will be present at all times to answer any questions and to ensure that Spanish speaking participants fully understand. As noted previously, each participant will be consented in-person in the language which they are most comfortable.

e-Consent

Verbal consent for participation will first be obtained via a phone call or in-person. During this phone call or in-person contact, eligibility will be determined by the research team at SCCC-Behavioral Community-Based Research Shared Resource department and documented in Ripple for recruitment tracking purposes only. Following verbal consent for participation, the participant will be scheduled for either a virtual or in-person consent meeting, depending on their format preferences. The consent form and all research documents will be available in English, Spanish, and Haitian-Creole and the consent process will be conducted in their preferred language.

Remote consent will also be used for participants who prefer to conduct all screening and interviews via Zoom. Once a qualified person expresses their willingness to participate, the staff will contact the person via Zoom, to explain the research study to the participant and answer any questions that may arise, and to proceed to remotely Consent patient via RedCap.

The CTSI e-Consent Template will be used for both remote and in-person consent. We will send a copy of the consent document to the participant a few days before the discussion in order to allow them to read, develop a list of questions, and discuss the research with family or friends. A printed copy will be provided to in-person participants. We will arrange a Zoom meeting that includes the person obtaining consent, the participant, and any additional people requested by the participant (e.g., relative, friend). During the meeting we will review and explain the information in the consent document, answer any questions the participant has about the study, ask the participant questions about the study to confirm their comprehension, and ask the participant if they consent to participate. If the participant agrees, then they will be asked to sign and date the consent document electronically. Then we will explain to the participant that they will receive a copy of the signed documents via email.

24) Process to Document Consent in Writing

Consent will be documented in writing prior to initiating onsite data collection. Please see the attached consent form.

25) Drugs or Devices

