Primary Outcome Measure Title: Change in Heart Rate Variability (HRV)

Primary Outcome Measure Description: HRV will be measured with an H10 chest strap device (Polar, Finland)

Primary Outcome Measure Timeframe: at visits 2 and 3, Baseline (15 minutes pre taVNS application) to 15 minutes post 1 hour application of taVNS

Secondary Outcome Measure Title: Change in EXPECT questionnaire scores

Secondary Outcome Measure Description: scores ranging from 0-40 with higher scores representing greater expectations for pain relief

Secondary Outcome Measure Timeframe: at visits 2 and 3, Baseline (pre taVNS application) and repeated post 1 hour application of taVNS

10) Arms and Interventions

All participants will be educated on both neurostimulation modalities (taVNS and TMS). This study will include 2 arms. Group 1 will receive a supplemental video on taVNS, in addition to consent forms and brochures describing both modalities.

Group 2 will only receive the consent forms and brochures describing both modalities. While all participants will provide important feedback on consent forms and brochures for both modalities, Group 1 will provide additional feedback specific to the taVNS video they watched.

We will assess the impact of the taVNS video (by comparing Group 1 to Group 2) on participant expectations and intended effects with a single 60-minute bout of taVNS.

11) Procedures Involved*

Black and Hispanic patients with persistent pain will be recruited for a 2-phased mixed methods study. All data collection will take place at the Lynn Rehabilitation Center. In the first phase, participants will be educated on two neurostimulation modalities (taVNS and TMS).

Educational materials will include 1:1 discussion of a typical consent form for each modality, a brief (2 page) description with pictures for each modality, and the brief video for taVNS for those randomly allocated to Group 1. *The development of these educational resources is a primary objective of this project, and the first few months will be spent consulting with experts to develop these educational resources and to produce the videos.*

Structured interviews and questionnaires will be used to examine participants interest in participating in research for each of the modalities, gather their feedback on each educational tool, and to determine factors that influence their interest. This first phase will take place in a single session, and the session is anticipated to take ~2 hours to complete.

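### Does section 22, which pays for visits 1 and 2 but does not name visit 3, put the crossover data at risk?

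*Combined protocol and SAP*

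**What the plan says.** Section 22 (Economic Burden to Subjects) sets a total of $250 per participant to offset cost and time. It itemizes $50 on completing visit 1 and, in dollars, "200 for completion of visit 2". Visit 3 is not mentioned.

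The schedule elsewhere has three visits:

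- Section 8: "Each participant will complete 3 visits for a total of ~10 hours".
- Section 11, first phase: "This first phase will take place in a single session, and the session is anticipated to take ~2 hours to complete".
- Section 11, second phase: "The second phase will be completed in two sessions that are anticipated to last ~4 hours each".
- Section 11, on who crosses over: "only Group 2 will receive both active and sham taVNS in a randomized crossover design". The table there puts 12 participants in that group, 6 per sequence, with the switch at visit 3. For the 12 in the taVNS video group, visit 3 is a one-week follow-up.
- Section 9 times the primary outcome, change in heart rate variability, "at visits 2 and 3, Baseline (15 minutes pre taVNS application) to 15 minutes post 1 hour application of taVNS".

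The protocol does not always separate the two stimulation visits. Section 13 says: "Safety information will be collected during the taVNS trial study visit", in the singular. Section 23 divides the study into a mixed-methods phase and a trial phase.

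**The concern.** Taken at face value, a participant has earned the full $250 by the end of visit 2 and is then asked back for another on-site session of about 4 hours for nothing. Visit 3 is about 40% of the total time (4 of 10 hours).

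For the brochures-only group it is also where the within-person comparison is completed. Someone who stops after visit 2 gives no active-sham pair for Aim 3. If that person was assigned sham first, the only active session is lost too, and with it the heart rate variability contribution to the Aim 2 comparison of groups. With 12 crossover participants in the table, a few such losses would be noticeable. A payment plan that stops one visit early would be an odd choice in a study whose stated purposes include learning how to retain underrepresented participants.

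**Working it through.** **1. Reproduce the stated total.** Section 22: $50 + $200 = $250. The sum agrees with the total, so $250 − $250 = $0 is itemized for visit 3.

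**2. Hourly rates under the two readings.** Hours come from section 11: about 2 for visit 1 and about 4 each for visits 2 and 3. The sum, 2 + 4 + 4 = 10, agrees with section 8.

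| Reading | Visit 1 | Visit 2 | Visit 3 |
|---|---|---|---|
| Literal: $200 is for visit 2 only | 50/2 = $25/h | 200/4 = $50/h | 0/4 = $0/h |
| Phase: $200 covers visits 2 and 3 | 50/2 = $25/h | 200/8 = $25/h | 200/8 = $25/h |

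The overall rate is 250/10 = $25/h. The phase reading gives that rate throughout. The literal reading doubles it at visit 2 and drops it to zero at visit 3, and no reason is given for that. The singular visit in section 13 and the two phases in sections 11 and 23 point the same way. This favours a slip of the label, without proving it.

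**3. What a lost visit 3 would cost, whatever the cause.** The documents give no attrition rate, so losses of a = 10%, 20% and 30% at visit 3 are assumed here for illustration only.

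- Aim 3, starting from 12 pairs. The standard error of the mean active-sham difference is multiplied by 1/√(1 − a): 1/√0.9 = 1.054, 1/√0.8 = 1.118, 1/√0.7 = 1.195. Each lost participant removes 1/12 = 8.3% of the pairs.
- Aim 2 (heart rate variability), 12 per group, with loss only among the 6 sham-first participants. Active sessions in the brochures-only group are n₂ = 6 + 6(1 − a) = 11.4, 10.8, 10.2. The standard error is multiplied by √[(1/12 + 1/n₂)/(2/12)] = 1.013, 1.027, 1.043.
- Section 7 gives "Enrollment: 28" against 24 in the table. If the difference is a dropout allowance split 14 per group (assumed; the protocol does not explain it), the Aim 3 standard error relative to 12 complete pairs is √[12/(14(1 − a))] = 0.976, 1.035, 1.107.

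These figures describe missing visit 3 data in general. None is the effect of the wording in section 22, because nothing in the documents says how far return depends on payment. On the phase reading the wording has no such effect, since the payment already covers visit 3.

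**4. Would splitting the $200 help?** A $100/$100 split over visits 2 and 3 keeps $25/h at each visit. If the $200 is already earned only on finishing the phase, the split cuts the amount that depends on returning for visit 3 from $200 to $100. On the better-supported reading it would weaken the incentive it was meant to create.

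**5. Bias.** The same terms apply to both groups and both sequences, so section 22 gives no mechanism by which payment would favour one over another.

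**The case for a change.** The strongest case for acting is that section 22 needs correcting on either reading. The section 11 table defines visits 2 and 3 as separate sessions, so the word used in section 22 has a definite meaning in this protocol, and on that meaning visit 3 is unpaid. The phase reading is an inference from round hourly rates. For a participant who stops after visit 2, the text does not settle whether $200 or nothing more is owed, and section 23 promises that withdrawal has no negative consequences. Visit 3 is also an on-site visit of the kind the payment is meant to offset, and one clarifying clause would cost nothing.

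Most of this stands as a matter of administration. The sentence does not match the schedule, and what is owed after visit 2 should be clear to staff and participants. The consent form, which states terms to participants, is not among the documents supplied and may already settle it.

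What does not stand is the step from an unclear sentence to damaged data. That step needs the less-supported reading, plus an effect of payment on return that no section describes. The exposure is also narrower than it first looks. Visit 3 is a crossover period for only 12 of the 24 participants in the table. Aim 3 is labelled exploratory in section 3. The Aim 2 expectation score is also collected before stimulation at visit 2 (section 9), so it survives a missed visit 3.

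**Conclusion.** The mismatch is real but clerical. Section 22 allots all $250 to two named visits in a three-visit study, and the likeliest explanation is that the second label was meant for the whole stimulation phase, where $200 over 8 hours matches the $25 per hour that applies everywhere else. On that reading visit 3 is covered, and clearer wording would alter no endpoint, estimate or conclusion.

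The literal reading cannot be excluded from the text. Even so, its cost to the trial cannot be put in figures. The illustrative rise in standard error of 5% to 20% for Aim 3 and 1% to 4% for Aim 2 rests on assumed losses that the documents do not link to payment. No gain in precision and no removal of bias has been shown, and redistributing the money could reduce the incentive to return. The sponsor can confirm what the $200 covers, and that the consent form agrees, as ordinary housekeeping. The design, payment total and analysis stay as they are. This conclusion assumes that the consent form does not contradict the phase reading.
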